5.7.2.2 Tumor control rates at 3, 6, 9, 12 months

It is defined as the percentage of patients in Complete Response or Partial Response or in stability at the given time.

Patients for whom tumor assessments would not allow classification will be reviewed by a clinician.

Patients who died will be considered uncontrolled.

5.7.2.3 Progression-free survival (if Phase III not done)

It is defined as the time interval between the date of randomization and the date of first progression or death (regardless of cause). Progression is defined as progression of lesions according to RECISTm criteria, the appearance of a new liver lesion or an extra-hepatic lesion.

Since progress can be documented on the in-process assessments or the monitoring form, the definition in 5.7.2 applies. The dates to be considered are the dates of the CTs.

Live patients without progression will be censored at the date of the last informative examination or at the date of last news if a surveillance sheet is provided not documenting progression or at the point date.

Clinical progressions will not be taken into account, based on the principle that for this type of pathology, a progression in imaging is necessarily associated with a clinical progression.

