5.7.2.4 Disease-free survival (if Phase III not done)

It is defined as the time interval between the date of randomization and the date of progression, or the date of a second cancer, or death (from any cause).

Since progression or second cancer may be documented on in-process assessments or the surveillance form, the definition in Section 5.7.2 applies. The dates to be considered are the dates of the CT scans.

Living patients without progression or second cancers will be censored at the date of the last informative review or at the date of last news if a surveillance form is provided that does not document progression or second cancers at the point date.

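### PFS and DFS can be censored at a date that rests on no scan, so follow-up without imaging counts as progression-free; the bias is upward and its size is unknown

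*SAP*

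**What the plan says.** SAP 5.7.2.3 makes imaging the only route to a progression event: "Progression is defined as progression of lesions according to RECISTm criteria, the appearance of a new liver lesion or an extra-hepatic lesion". On timing it says "The dates to be considered are the dates of the CTs", and it adds "Clinical progressions will not be taken into account". Death from any cause is the other PFS event.

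For patients without an event, the section lists three censoring dates:

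- the last examination: "Live patients without progression will be censored at the date of the last informative examination";
- last news: "at the date of last news if a surveillance sheet is provided not documenting progression";
- the point date.

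SAP 8.1.2 defines last news as the date on the monitoring form, falling back on the last examination or last treatment if that is missing. It does not mention imaging.

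SAP 5.7.2.4 (DFS) adds second cancer as an event and again allows censoring "at the date of last news if a surveillance form is provided that does not document progression or second cancers". There the point date follows without a connecting word, so it is unclear whether it is a separate option.

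The protocol, Section XVI, censors relapse-free and disease-free survival of living patients at the last follow-up, also without reference to a scan.

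**The concern.** A patient should count as at risk of progression only while a progression could be found. Here it can be found only on a scan, but the censoring date may come from a form that need not report one. A patient who stops imaging and still attends visits stays in the risk set, and until death nothing can end the progression-free time.

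The loose order of the dates adds to this. Two programmers could code different endpoints from the same sentence, and SAP 9.2.3 requires double programming only for the main criterion.

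At stake is how far the PFS and DFS curves can be believed. The phase II primary endpoint (bleeding or liver failure) and the phase III primary endpoint (overall survival) are not affected.

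**Working it through.** **No figure to reproduce.** The documents give no PFS rate, event count or missed-scan rate. The point rests on the text; the numbers below only illustrate it.

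**Direction.** Take a patient whose progression would be found at time *s* with complete imaging. Without that scan, and with contact continuing, the record shows a later detection, a later death, or censoring at a last-news date at or after *s*. In each case the event at *s* is replaced by something no earlier, so the Kaplan-Meier curve can only rise.

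**Opportunity.** Protocol Section XI schedules routine imaging every 3 months for 2 years and clinical visits every 6 weeks in year 1. A form dated after the last scan is therefore possible even with full adherence.

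**Illustrative size.** Simulation of 200,000 patients per scenario.

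- From the protocol: scans every 3 months to month 24, then every 6 months (the extra post-TACE scans are left out); visits every 6 weeks in year 1, every 3 months in year 2, then every 6 months.
- Assumed: exponential time to imaging progression with median 6, 9 or 12 months; death without progression 1% per month; mean survival after progression 12 months; administrative follow-up 12-36 months; 0, 10, 20 or 30% of patients stop scans at a uniform time in months 0-12 but keep attending visits, the last visit being last news.
- Last-scan censoring counts deaths within two scan intervals of the last scan.

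Overstatement = PFS(last news) − PFS(complete imaging). At 12 months:

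| Median (months) | Stop scans | Complete imaging | Last news | Last scan | Overstatement (points) |
|---|---|---|---|---|---|
| 6 | 10% | 22.1% | 24.4% | 21.8% | 2.3 |
| 6 | 20% | 22.3% | 27.0% | 21.6% | 4.7 |
| 6 | 30% | 22.3% | 29.3% | 21.3% | 7.0 |
| 9 | 10% | 35.2% | 37.3% | 34.8% | 2.1 |
| 9 | 20% | 35.2% | 39.4% | 34.4% | 4.2 |
| 9 | 30% | 35.2% | 41.3% | 33.8% | 6.1 |
| 12 | 10% | 44.3% | 46.1% | 43.9% | 1.8 |
| 12 | 20% | 44.4% | 47.9% | 43.4% | 3.5 |
| 12 | 30% | 44.4% | 49.7% | 42.9% | 5.3 |

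If nobody stops scans, the three rules agree. Over the same nine scenarios the overstatement is 0.8 to 4.1 points at 6 months and 1.6 to 5.5 points at 24 months. The largest shift in the median is from 6.0 to 7.2 months, and in most scenarios it does not move. Last-scan censoring is itself 0.3 to 1.5 points low at 12 months in these nine scenarios.

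**Which time points exist.** SAP 7.2.2 sets the phase II cut-off one week after the last chemoembolization of the last phase II patient. At the planned pace:

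- accrual: 70 / 7.5 = 9.3 months;
- drug lead-in before the first TACE: 7-10 days = 0.2-0.3 month;
- three TACE 6-8 weeks apart: 12-16 weeks = 2.8-3.7 months;
- one further week: 0.2 month.

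The sum is about 12.6 to 13.6 months after first inclusion. Patients with 12 months of potential follow-up number about 0.55 × 7.5 ≈ 4 to 1.57 × 7.5 ≈ 12 of 70. The 24-month figures have meaning only if phase III runs or phase II accrual is much slower than planned.

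**The case against.** The strongest reply is that the monitoring form is itself a place where imaging results are recorded. SAP 5.7.2.3 says: "Since progress can be documented on the in-process assessments or the monitoring form, the definition in 5.7.2 applies". A form that documents no progression may therefore be a negative scan report. The case report form is not among the documents, so this cannot be excluded, and if it holds the credited time is close to zero. What remains is that the SAP does not require it.

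On precedence, the last informative examination comes first in the list, last news applies only when a form is supplied, and SAP 5.7.4 uses an earlier-of convention for quality of life. A workable reading exists, but 5.7.2.3 and 5.7.2.4 do not state it.

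Two stronger readings are tempting. A reader might infer that the rule tilts the PFS comparison towards sunitinib, because toxicity could end scanning sooner in that arm. The documents do not support this. Both SAP sections are headed as applying when phase III is not done, and SAP 5.7.7 and 8.7 then rule out comparisons between arms. If phase III runs, SAP 8.7.1 does compare PFS by logrank test, but nothing shows that scan loss would differ by arm. A reader might also infer that a patient without scans can never have a PFS event. That is wrong, because death counts.

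It is fair, too, that moving to last-scan censoring departs from the protocol's last-follow-up rule, and that DFS needs separate thought because second cancer is also an event.

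**Conclusion.** The point stands in a limited form. As written, SAP 5.7.2.3 and 5.7.2.4 allow follow-up without imaging to count as progression-free, and the error can only be upward. The size cannot be read from the documents: about zero if every form accompanies a scan, and roughly 2 to 7 points at 12 months if 10-30% of patients stop scans in year 1 while staying in contact. That range depends wholly on the assumed scan loss, and also on the assumed progression and death rates.

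If the trial ends at phase II, the consequence is optimistic descriptive curves for secondary endpoints, with few patients followed to 12 months at the planned pace. A distorted comparison would need phase III to run and scan loss to differ between arms. The correction is standard and cheap, so it is worth making before the database is frozen.

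**What to change.** Change SAP 5.7.2.3 so that living patients without progression are censored at the last evaluable tumour imaging showing none, on or before the point date, or at randomisation if there is no post-baseline scan. This also settles the order of the dates.

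State how deaths after missed scans are handled. One option is to count a death within two scheduled scan intervals of the last scan and otherwise censor at that scan, with all deaths counted in a sensitivity analysis.

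Apply the same rule to the progression component of DFS, with a stated rule for how second cancers are ascertained and dated and how they enter the censoring date.

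Align the last-follow-up censoring of relapse-free and disease-free survival in protocol Section XVI. Keep last-news censoring as a sensitivity analysis, and report by arm the time from last scan to last news, which shows directly whether the issue matters.

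The cost is a few SAP sentences, which SAP 7.3 permits before database freeze, plus the protocol alignment. Some patients are censored earlier, so intervals widen slightly.

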5.7.2.4 Disease-free survival (if Phase III not done)

It is defined as the time interval between the date of randomization and the date of progression, or the date of a second cancer, or death (from any cause).

Since progression or second cancer may be documented on in-process assessments or the surveillance form, the definition in Section 5.7.2 applies. The dates to be considered are the dates of the CT scans.

Living patients without progression or second cancers will be censored at the date of the last informative review or at the date of last news if a surveillance form is provided that does not document progression or second cancers at the point date.

5.7.2.5 Overall survival (if Phase III not done)

Overall survival is defined as the time from the date of randomization to the date of death (from any cause).

Patients lost to follow-up or alive at the time of analysis will be censored at the last news date or the point date.

This time will also be used to calculate the median follow-up time.

5.7.3 Secondary tolerability criteria

Tolerance to treatment will be assessed by:

- chemo-embolization
- duration of sunitinib/placebo treatment, number of tablets administered, dose reductions, treatment discontinuations and their causes ;

The duration of the treatment (converted into months) will be calculated by adding the cycle durations: (cycle end date - cycle start date) + 1

- Toxicities, collected at the end of each treatment cycle, will be described according to the NCI-CTC version 4.0 criteria and their grade;
- the time to onset of grade 3-4 toxicity will be assessed;

It is defined as the time interval between the date of randomization and the date of first grade 3-4 toxicity estimated by the cycle start date + 2 weeks. Patients without Grade 3-4 toxicity at the earlier of the point or last date will be censored at the point or last date;

- The description of SAEs (analysis of pharmacovigilance)

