- Number and percentage of patients with at least one side effect
- Number and percentage of patients with at least one grade 3-4 side effect
- Number and percentage of patients with at least one SAE
- Number and percentage of patients with at least one side effect and grade 3-4 side effect due to the treatment.
- Number and percentage of patients with at least one side effect that lead to cessation of the treatment

Time to the first occurrence of grade 3-4 toxicity will be estimated by the Kaplan-Meier method.

XVII. POPULATIONS FOR ANALYSIS

The populations for the analysis are defined as follows:

Intention to treat: The intention to treat population will be composed by all included patients who were randomised to one of the two treatment groups, and patients will be analysed according to the treatment to which they were randomised. This will be the primary population for all analyses of efficacy data and baseline characteristics.

Per protocol: The per protocol population excludes patients randomised who did not receive any trial medication or who had a major violation of the protocol inclusion or exclusion criteria. Patients will be analysed according to the treatment to which they were randomised.

Safety: The safety population will include all patients who received at least one dose of trial medication. Only patients with clear documentation that no trial medication was received may be excluded. Patients will be analysed according to the treatment, which they actually received. This will be the population for the analysis of all safety data.

XVIII. ADVERSE EVENT REPORTING

1. Definition

An adverse event (AE) is defined as any untoward medical occurrence in a patient or clinical investigation subject administered a pharmaceutical product, which does not necessarily have a causal relationship with this treatment. An AE can therefore be any unfavourable and unintended sign (including an abnormal laboratory finding), symptom, or disease temporally associated with the use of a medicinal (investigational) product, whether or not related to the medicinal (investigational) product.

AE include the following:

- All suspected adverse medication reactions,
- All reactions from medication overdose, abuse, discontinuation, sensitivity, or toxicity.
- Apparently unrelated illnesses, including the worsening of a pre-existing illness.

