- Injury or accidents. Note that if a medical condition is known to have caused the injury or accident, the medical condition and the accident should be reported as two separate AE.
- Abnormalities in physiological testing or physical examination findings that require clinical intervention or further investigation (beyond ordering a repeat [confirmatory] test).
- Laboratory abnormalities that require clinical intervention or further investigation (beyond ordering a repeat [confirmatory] test) unless they are associated with an already reported

clinical event.

Laboratory

abnormalities associated with a clinical event (e.g. elevated liver enzymes in a patient with jaundice) should be described in the comments of the report of the clinical event rather than listed as a separate AE.

2. Reporting

All AE, as defined above, encountered during the clinical trial as well as any **Serious Adverse Events** (SAE) will be reported in the appropriate section of the CRF. It is important that this includes the duration of the AE (onset/resolution dates), the severity, the relationship to the drug and any concomitant treatment dispensed (or other action taken). Adverse event data should be obtained through observation of the patient, from any information volunteered by the patient, or through patient questioning. The general type of question asked could be similar to: “Do you have any health problems?” or “Have you had any health problems since your last clinic visit?”

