5.7 Judgement criteria for la phase II

5.7.1 Main criterion

The primary endpoint of la phase II is the rate of bleeding and/or severe liver failure within one week of chemoembolization sessions (TACE), over all chemoembolization sessions for a patient. The precise definition of bleeding and liver failure to be retained is given in the protocol with amendment 3 :

- Severe liver failure is defined by the occurrence of at least one of the following complications:
 - encephalopathy;
 - clinical ascites; in case of clinical ascites already present at inclusion and persistence of ascites at the time of evaluation for liver failure, an independent committee will have to judge from the case report whether ascites has evolved since inclusion and should be counted as an event in the definition of the primary endpoint or not; if clinical ascites is present at inclusion, it will be graded according to NCI-CTC v4 and reported through a CID; during follow-up, clinical encephalopathy and ascites will be graded according to NCI-CTC v4 and will appear on form 3.1 of the case report form in the other toxicities tab
 - bilirubin levels greater than or equal to 50 mg/L (85.5 μ mol/L);
 - TP \leq 40%;
- bleeding : (definition p14 of the protocol)

These events count as primary endpoints if they occur within 1 week of chemoembolization, i.e., between D0 and D7 inclusive.

In the case of an event counting for the primary endpoint after D7, it will be recorded in the case report form 3.1 in the column after D5 only if the investigator considers that this event is related to the TACE, and the day must then be filled in. For events recorded after D7 in the case report form, an independent committee will meet to decide whether or not this event counts in the definition of the primary endpoint.

Patients who did not receive their oral treatment will still be counted in the primary endpoint; however, a very precise description of the reason for not taking the oral treatment will be made.

Patients who did not have chemoembolization will be excluded from this analysis (modified ITT).

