8.6.1.3 Toxicity analysis

Toxicities will be described by treatment arm according to NCI-CTC version 4.0 criteria:

- by grade and type at the end of cycles during TACE treatment, over all cycles and during follow-up;
- Patients with at least one grade 3-4 toxicity of any type (during cycles including TACE and over all cycles), with 95% confidence interval;
- Time to Grade 3-4 toxicity will be (Toxicities collected during HEC and cycles) plotted with 95% confidence intervals and rates at different times (time to be adapted according to data) and their 95% confidence intervals.

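### SAP 5.7.3 dates every first grade 3-4 toxicity at cycle start plus two weeks, even where an onset day is recorded, which distorts the within-cycle rates of a secondary descriptive curve

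*SAP*

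**What the plan says.** SAP 5.7.3 measures this endpoint from randomization to the first grade 3-4 toxicity, whose date is "estimated by the cycle start date + 2 weeks". The rule applies to every event and is not limited to missing dates. The same list describes how the data arise: "Toxicities, collected at the end of each treatment cycle, will be described according to the NCI-CTC version 4.0 criteria and their grade".

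SAP 8.6.1.3 says what the curve contains and what will be read from it: "Toxicities collected during HEC and cycles) plotted with 95% confidence intervals and rates at different times". I read HEC as chemoembolization, in line with SAP 8.5.1.3. Two sources therefore feed the curve: the post-TACE charts and the cycle forms.

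Protocol XVIII.2, on what the CRF must hold for each adverse event, says: "It is important that this includes the duration of the AE (onset/resolution dates), the severity, the relationship to the drug". Protocol XVI plans the endpoint without any imputation: "Time to the first occurrence of grade 3-4 toxicity will be estimated by the Kaplan-Meier method".

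For a primary-endpoint event after D7, SAP 5.7.1 has it entered on form 3.1 "only if the investigator considers that this event is related to the TACE, and the day must then be filled in". The SAP's general convention for partial dates (8.1.4) fills in a day only when the day is missing.

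**The concern.** The Protocol asks for a date, and the SAP replaces it with a computed one without giving a reason. For the cycle forms, collection at cycle end may be the reason. It does not cover the post-TACE charts, where at least some events have a known day that the rule, read literally, would overwrite.

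What is at stake is the shape of the curve. All first events of a cycle fall on one cycle day, so a rate quoted at a time inside a cycle depends on which side of that day it lies. The confidence intervals treat the assigned dates as observed. Two arms with different onset timing within the same cycle would look alike: true onsets 3 and 27 days after cycle start are both placed at 14. A patient who dies or is last seen within 14 days of cycle start could also have an event dated after that point.

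**Working it through.** The plan gives no sample size, power or event count for this endpoint, so there is no figure to reproduce. The check has two parts: the dating error, and its effect on the curve.

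**Inputs from the documents**
- Assigned date: cycle start + 14 days (SAP 5.7.3).
- Cycle: 28 days on drug, 14 off, 42 in all (Protocol IX).
- TACE: 7 to 10 days after the start of drug in that cycle (Protocol IX).
- Post-TACE window: D0 to D7 (SAP 5.7.1).

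**Dating error.** Let x be the true onset in days after cycle start. Error = 14 − x; positive means dated too late.
- Onset on drug, x = 0 to 27: error +14 to −13. With uniform onset (assumed), the mean is 14 − 13.5 = +0.5 days and the mean absolute error is (105 + 91)/28 = 7.0 days.
- Onset anywhere in the cycle, x = 0 to 41: error +14 to −27. With uniform onset, the mean is 14 − 20.5 = −6.5 days and the mean absolute error is (105 + 378)/42 = 11.5 days.
- Onset on TACE D0 to D7: with TACE at day 7, x = 7 to 14 and the error is +7 to 0. With TACE at day 10, x = 10 to 17 and the error is +4 to −3.

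**Effect on the curve.** The documents give no per-cycle rate, so I assume that a proportion q of event-free patients has a first grade 3-4 toxicity in each 42-day cycle, with q from 10% to 40%. I also assume a constant hazard, no censoring, and time counted from the start of cycle 1. Then:
- Exact incidence by day d = 1 − (1 − q)^(d/42).
- Under the rule, incidence is 0 up to day 13 and q from day 14 to day 55.
- Exact median = 42 × ln 2 / [−ln(1 − q)]. Under the rule, the median is day 14 of the first cycle by whose end incidence reaches 50%.

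| q | Day 13: exact / rule | Day 14: exact / rule | Day 28: exact / rule | Day 42: exact / rule | Median: exact / rule |
|---|---|---|---|---|---|
| 10% | 3.2% / 0% | 3.5% / 10% | 6.8% / 10% | 10% / 10% | 276 / 266 days |
| 20% | 6.7% / 0% | 7.2% / 20% | 13.8% / 20% | 20% / 20% | 130 / 140 days |
| 30% | 10.5% / 0% | 11.2% / 30% | 21.2% / 30% | 30% / 30% | 82 / 56 days |
| 40% | 14.6% / 0% | 15.7% / 40% | 28.9% / 40% | 40% / 40% | 57 / 56 days |

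For q = 20%, day 14 is 1 − 0.8^(1/3) = 7.2%. For q = 30%, incidence at the end of cycle 2 is 1 − 0.7² = 51%, so the median under the rule is 42 + 14 = 56 days, against 42 × 0.693/0.357 = 82.

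The curve agrees with the exact one at cycle ends and departs from it in between. The median moves by 1 to 26 days, in either direction.

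**The case against.** The best defence is that the CRF is not among the documents. The Protocol's instruction on onset dates is general, while the SAP describes toxicities collected by grade at the end of each cycle. If the cycle form is a grade grid without dates, the rule is an ordinary imputation for interval data: prespecified, the same in both arms, and placed at the middle of the 28-day dosing period. This stands as far as the cycle forms go. It does not explain an unconditional rule, nor its reach over post-TACE events whose day is known.

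It also stands that SAP 5.7.1 requires a day only for certain events on form 3.1. Protocol XI and XII add blood tests on set days around TACE and daily monitoring in hospital, which makes further day-level data likely but does not prove it for every toxicity. SAP 8.6.1.3 brings post-TACE toxicities into the curve without saying how they are dated; 5.7.3 is the only rule given.

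A reader might infer that the trial's main safety question is compromised because events before and after TACE can no longer be told apart. The documents do not support that. The phase II question is severe bleeding or liver failure within a week of TACE, counted D0 to D7 (SAP 5.7.1) and analysed as a proportion of patients and by TACE session (SAP 8.4). None of that uses the assigned date. Post-TACE toxicities are also tabulated separately (SAP 8.5.1.3), and a curve of first toxicity from randomization would not separate the two periods even with exact dates.

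**Conclusion.** The point holds as a limited one. The rule should not override a recorded date, and as written it does. The error is at most 14 days late and 27 days early in a nominal 42-day cycle; a prolonged cycle could be further out. For onset on TACE D0 to D7 it is only +7 to −3 days. Rates read inside a cycle, and the median, are distorted. The sizes in the table rest on assumed event rates and a constant hazard, but the step pattern follows from the rule itself. Because time runs from randomization, each patient's interval to cycle start will blur the steps somewhat. Agreement at cycle ends is exact only without censoring; with censoring, the risk sets shift slightly.

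The consequence is small. This is one secondary curve, described by arm with no test in the SAP. The proportion with at least one grade 3-4 toxicity and the phase II primary endpoint do not depend on this date.

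A reader might go further and call the dates fabricated, or say the CRF certainly holds an onset date for every toxicity. Neither is supported: the cycle is observed and the rule is declared in advance, and the documents show only that the Protocol requires onset dates.

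**What to change.** In SAP 5.7.3, set an order for dating the first grade 3-4 toxicity:
1. The recorded onset date, where there is one.
2. For post-TACE forms, the TACE date plus the recorded day.
3. Cycle start + 2 weeks only when neither exists, capped at death or last news.

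Report by arm how many events were dated by step 3. A sensitivity analysis placing those events at cycle start and then at cycle end would show how far the curve depends on them.

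If the cycle forms hold no onset dates, state this in the SAP and report cumulative incidence by cycle, which is what such data support.

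The cost is minor programming and no new data collection, since the order uses only dates already recorded. It should be settled before the database is frozen, as SAP 7.3 requires for changes to the plan.
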